9.3. Level of Significance

No formal efficacy hypotheses will be tested. All CIs will be 95%.

9.4. Statistical Analyses

9.4.1. Primary Analyses

Phase 1: The safety and tolerability of epacadostat in combination with durvalumab will be evaluated. See Section 9.4.3 for more details. Descriptive statistics (eg, mean, standard deviation, range) will be derived where appropriate. Subject enrollment, disposition, demographics, and medical history will be summarized at baseline. The rate of DLTs will be summarized for each cohort. Dose exposure and density will be calculated for each cohort. Safety and disease response data will be compared over time to assess change from baseline, during treatment, and follow-up. Pharmacokinetic [REDACTED] data will be analyzed with appropriate standard nonlinear analytic software.

Phases 1 and 2: The proportion of subjects with objective response by mRECIST v1.1 will be summarized. A subject is considered an objective responder as assessed by mRECIST v1.1 if he or she has an overall response of CR or PR at any postbaseline visit. The proportion of responders within each treatment group will be estimated with 95% CIs by treatment group. Confidence intervals will be calculated based on the exact method for binomial distributions.

9.4.2. Secondary Analyses

For objective responders, the duration of response is the time from the first overall response contributing to an objective response, to the first overall response of PD (by mRECIST v1.1) occurring after the first overall response contributing to the objective response. Median duration of response and time to disease progression will be estimated using the Kaplan-Meier method. Confidence intervals for median survival time will be calculated using the method of Brookmeyer and Crowley (1982), which is the default method within SAS v9.1.

Progression-free survival data will be analyzed by the Kaplan-Meier method, treating subjects with no observed death or progression censored at their last date known to be alive and progression-free.

9.4.3. Safety Analyses

The principal analysis will be based on the safety evaluable population, according to treatment assignment.

Adverse events will be coded by the MedDRA, and incidences will be tabulated by preferred term and system organ class for all events, related events, and events \geq Grade 3. Severity of AEs will be based on the CTCAE scale as indicated in Section 8.1.1. Quantitative safety variables and their changes from baseline (laboratory, vital signs) will be summarized with descriptive statistics. Clinically significant abnormal values will be flagged and tabulated based on predefined criteria.

Exposure will be analyzed by describing dose intensity, which is defined as the dose received, divided by the dose planned, over a given time interval. This will be done by cycle as well as overall cycles received for durvalumab + epacadostat and durvalumab alone. For each cycle,

incidences of dose reductions and cycle delays will also be tabulated by reason for the reduction or delay. The percentage of subjects with any delay and/or reduction will also be calculated.

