5.6.2. Criteria and Procedures for Interruption or Dose Reduction

In some circumstances, it may be necessary to temporarily interrupt treatment as a result of adverse experiences that may have an unclear relationship to study drug.

Table 8 summarizes the dosing actions for epacadostat and durvalumab that must be implemented with the indicated related AEs. Additional information related to dose changes and AE management for irAEs can be found in Section 5.6.3.

In general, treatment with both study drugs should be withheld for \geq Grade 3 irAEs or non-irAEs and may be withheld for \geq Grade 2 irAEs. Additional details for irAEs are provided in Section 5.6.3.

If a criterion for dose reduction of epacadostat is met, refer to Table 9 to determine the appropriate dose for the subject. There will be no dose reductions of durvalumab allowed for the management of toxicities of individual subjects (exception noted in Section 5.6.1). Doses of

durvalumab may be delayed for toxicity management. In general, study treatment should be discontinued for toxicities that do not resolve to Grade 1 or less within 4 weeks of onset. Exceptions to this must be discussed with the medical monitor.

Note: There may be some circumstances where, due to toxicity attributed to epacadostat, a subject may not tolerate the combination therapy but may benefit from monotherapy with durvalumab. These cases must be discussed and approved by the medical monitor before the subject may receive durvalumab monotherapy on study.

Any interruptions of > 4 weeks or for LFT abnormalities must be discussed with the medical monitor prior to resuming treatment.

Except in cases of emergency, it is recommended that the investigator consult with the medical monitor (or other representative of the sponsor) before temporarily interrupting therapy for reasons other than Protocol-mandated medication hold. Additionally, the investigator must notify the sponsor's medical monitor and study project manager via email before restarting study drug that was interrupted for > 4 weeks due to an AE.

Table 8: Dose Modification Guidelines of Epacadostat and Durvalumab for Non-Immune-Related Adverse Events

Adverse Event	CTCAE v4.0 Grade	Action With Respect to Epacadostat	Action With Respect to Durvalumab

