#### **4.1.6. Cycle Length and Duration**

Cycle 1 Day 1 is defined as the day of the first dose of INCB024360 or MEDI4736. One treatment cycle consists of 14 days. The first cycle of therapy is defined as the period beginning with the first dose of INCB024360 or MEDI4736 and ending the earlier of: (1) 14 calendar days (inclusive) later; or (2) permanent discontinuation of INCB024360. Subsequent cycles have Day 1 as the corresponding visit date associated with the corresponding cycle.

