### 6.4. Exposure

For subjects in the ITT and safety populations, descriptive statistics will be provided by cohort; number of cycles; duration of treatment; average daily dose (mg) and total dose (mg) of INCB024360; and number of doses, relative dose intensity (mg/kg), and average dose (mg/kg) of MEDI4736.

- **Number of Cycles:** Number of cycles for INCB024360 will be the number of cycles with a nonzero dose of INCB024360.
- **Duration of Treatment:** The number of study days between Day 1 and the last nonzero dose administration record of INCB024360 or MEDI4736 taken by the subject.
- **Number of Doses of MEDI4736:** Number of doses of MEDI4736 for a subject will be the number of administered, scheduled infusions of MEDI4736 recorded on the MEDI4736 Dosing CRF.
- **Average Doses of MEDI4736 (mg/kg):** The average dose of MEDI4736 (in mg/kg) will be the sum of the doses of MEDI4736 recorded on the MEDI4736 Dosing CRF divided by the number of doses of MEDI4736.

Treatment with MEDI4736 will be discontinued after 12 months of treatment. Discontinuation of MEDI4736 treatment may also be considered for subjects who have attained a confirmed complete response (CR). Subjects may continue on INCB024360 monotherapy at this time.

Subjects who then report radiographic disease progression will be eligible for re-treatment with MEDI4736 at the discretion of the investigator if no cancer treatment was administered other than INCB024360 and the subject meets the safety parameters listed in the inclusion/exclusion criteria. Subjects will resume therapy at the same dose and schedule at the time of initial discontinuation. Number of doses, average doses, and dose intensity for MEDI4736 in this re-treatment phase will be summarized separately and then combined with all previous doses.

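### Durvalumab dose intensity is computed over cycles received, so it stays at 100% however long infusions are delayed

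*Protocol*

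**What the plan says.** Protocol 9.4.3: "Exposure will be analyzed by describing dose intensity, which is defined as the dose received, divided by the dose planned, over a given time interval". The next sentence names the intervals: "This will be done by cycle as well as overall cycles received for durvalumab + epacadostat and durvalumab alone". The same paragraph adds that, per cycle, "incidences of dose reductions and cycle delays will also be tabulated by reason for the reduction or delay" and that "The percentage of subjects with any delay and/or reduction will also be calculated".

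Protocol 5.6.2: "There will be no dose reductions of durvalumab allowed for the management of toxicities of individual subjects". The only exception concerns subjects escalated from 3 mg/kg under 5.6.1. Delay is the permitted response.

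SAP 4.1.6: "One treatment cycle consists of 14 days", and "Subsequent cycles have Day 1 as the corresponding visit date associated with the corresponding cycle". An end is defined only for the first cycle.

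SAP 6.4 lists relative dose intensity for durvalumab with the unit mg/kg and no formula. It defines average durvalumab dose as the sum of doses divided by the number of doses given. For epacadostat, "Number of cycles for INCB024360 will be the number of cycles with a nonzero dose of INCB024360". The shell for Table 3.1.1.2 in SAP Appendix C has a percentage dose intensity for epacadostat, also undefined, and shows no dose-intensity row for durvalumab. The SAP was written on Protocol Amendment 1, but SAP 2.1 keeps it in force for later amendments.

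**The concern.** Relative dose intensity should show how much of the intended treatment subjects could take. For a drug whose dose cannot be lowered, toxicity shows up as lost time. If the denominator counts only the cycles that took place, and each cycle begins when the subject returns, lost time is removed from numerator and denominator alike. The statistic then says nothing about the one way in which durvalumab exposure is cut while treatment continues.

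Such delays are foreseen. Table 11 (Grade 2 enterocolitis) withholds both drugs, allows treatment to resume only after the steroid taper, and gives that taper at least 28 days; Table 12 (Grade 2 hepatitis) is similar where steroids are used. Safety and tolerability at the selected dose is a Phase 2 secondary objective. Protocol 5.5.1 also says that recurrent interruptions are to be considered when the Phase 2 dose is chosen. A figure that stays at 100% through long holds would make the combination look better tolerated than it was, most of all at the dose with the most holds.

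**Working it through.** The documents state no dose-intensity value, so there is nothing to reproduce. The delay patterns below are illustrative assumptions.

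**Inputs**
- Cycle length 14 days, with one durvalumab infusion per cycle (SAP 4.1.6; Protocol 5.1.2).
- Epacadostat twice daily (Protocol 5.1.1), so 14 × 2 = 28 doses per cycle.
- Durvalumab infusions are given in full when given.

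**Durvalumab: two denominators, for k infusions with D days of delay in total**
- Cycles received: (k × 10 mg/kg) / (k × 10 mg/kg) = 100% for any D.
- Elapsed time, first dose to last dose plus one interval: k / [(14k + D)/14] = 14k / (14k + D).

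| Infusions given | Delay | Cycles received | Elapsed time |
|---|---|---|---|
| 6 | one of 14 days | 100% | 84/98 = 85.7% |
| 6 | one of 28 days | 100% | 84/112 = 75.0% |
| 11 | one of 28 days | 100% | 154/182 = 84.6% |
| 13 | one of 14 days | 100% | 182/196 = 92.9% |
| 13 | every interval, 14 days (12 × 14 = 168) | 100% | 182/350 = 52.0% |

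The third row is the 26-week case: 182/14 = 13 infusions due, 11 given. The last row is a deliberate extreme.

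An infusion omitted at a visit that still counts as a cycle does lower the figure: 5/6 = 83.3% for one omission in six. It reads 100% only if that cycle is left out.

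**Epacadostat, planned dose taken as the assigned dose**
- 7-day hold inside a cycle: 14/28 = 50% for that cycle; over six cycles (6 × 28 − 14)/(6 × 28) = 154/168 = 91.7%.
- Reduction from 300 to 100 mg BID (Table 9): 100/300 = 33.3% for the cycle; if it starts at cycle 3 of 6, (2 × 300 + 4 × 100)/(6 × 300) = 55.6%.
- One of six cycles fully held: 5/6 = 83.3% if the cycle is counted, 100% if it drops out under the nonzero-dose rule.
- 14-day hold beginning exactly when the next cycle is due: 28/28 = 100% on a 14-day plan, 28/56 = 50% on elapsed time.

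Epacadostat intensity therefore responds to most interruptions and fails only for holds that coincide with cycle boundaries or fill whole cycles. Durvalumab intensity does not respond to delay at all.

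**The case against.** The definition in 9.4.3 refers to a time interval and does not say which, so an elapsed-time denominator is not excluded. SAP 4.1.6 gives no end for later cycles, so held days could be assigned to a lengthened preceding cycle. Both points are fair, but neither rescues the figure. The sentence after the definition names cycles as the intervals, and a lengthened cycle with one planned infusion still scores 100% unless planned dose is scaled by days, which nothing instructs. If both readings are open, two programmers could report 100% and 75% from the same records.

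Lost dose is also visible elsewhere: delays and reductions by reason, number of durvalumab doses, duration of treatment, days of exposure, and total and average daily epacadostat dose. This stands and limits the harm. It does not supply a subject-level ratio for durvalumab, and average durvalumab dose ignores delays in the same way.

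No decision uses dose intensity. The Phase 2 tolerability endpoint rests on adverse events, examinations, vital signs, ECGs and laboratory tests. Table 7 already treats toxicity-related loss of dose in the first 42 days as dose-limiting, and the pause rule in 9.6 uses Grade 3 or higher events. This stands in full.

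A reader might infer three stronger things that the documents do not support:
- That holds never lower dose intensity for either drug. Mid-cycle epacadostat holds, epacadostat reductions (if planned means assigned dose) and infusions omitted in a counted cycle all lower it.
- That the nonzero-dose rule in SAP 6.4 is the dose-intensity denominator. It defines only the number of cycles; carrying it over is an inference.
- That the plan adds mg/kg to mg. The combination and durvalumab-alone labels plausibly name regimens, since 5.6.2 allows durvalumab monotherapy after epacadostat toxicity.

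**Conclusion.** The concern holds for durvalumab. On the natural reading of Protocol 9.4.3 with SAP 4.1.6, its dose intensity stays at 100% for any delay followed by a full infusion; elapsed-time values for the patterns tried run from 92.9% down to 52.0%, with 75% to 85% for a single 28-day delay over 6 to 11 infusions. This assumes that planned dose is one full infusion per cycle received and that no infusion is partial or omitted in a counted cycle.

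For epacadostat the weakness is conditional: fully held cycles may drop out, depending on a denominator that the SAP does not state. The missing formula and the mg/kg unit for a ratio are plain gaps. Protocol 9.4.3 also names no epacadostat-only category, although legacy subjects could take it alone for up to 12 further months (5.4).

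The consequence is a tolerability summary that looks too favourable, not an error in any dose decision, stopping rule or efficacy result. It is worth correcting because the better method is specific and inexpensive.

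**What to change.** In Protocol 9.4.3 and SAP 6.4, define relative dose intensity as a percentage, separately for each drug: total dose received divided by the dose due at the assigned dose and schedule over elapsed calendar time, from the first dose of that drug to its last dose plus one dosing interval. State that held days, and delayed or omitted infusions, remain in the denominator, and that cycles with no epacadostat dose are not dropped. Replace the mg/kg unit, add a durvalumab row to the exposure shells, and show the legacy epacadostat-only period separately. Keep the planned tables of delays and reductions by reason.

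The cost is wording and minor programming, using dosing records that are already collected. Reported intensity will look somewhat less favourable.

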9.4.4. Clinical Laboratory Tests

The clinical laboratory data will be analyzed using summary statistics (eg, means and frequencies). In addition, distributions of key laboratory parameters (including hemoglobin, neutrophils, and platelets) will be plotted over time; these values will also be classified into CTCAE toxicity grades and tabulated. Descriptive statistics and mean change from baseline will be determined for vital signs at each assessment time. Vital sign results will be reviewed for clinically notable abnormalities.

9.5. Data Monitoring Committee

Not applicable.

9.6. Interim Analysis

An interim safety analysis is planned for Phase 2 after 16 subjects have been enrolled and treated for 8 weeks, and then approximately every 3 months thereafter. If the following is reported during these reviews, enrollment of subjects would be suspended until the sponsor determined the appropriate course of action and notified IRBs and regulatory authorities:

- $\geq 40\%$ of subjects have experienced an AE \geq Grade 3 that was attributable to the investigational agents.

No formal interim analysis for futility or efficacy is planned for this study.

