Approximately 140 to 192 subjects with advanced melanoma, NSCLC, SCCHN, TNBC, gastric or GE junction cancer, and TCC of the GU tract will be enrolled at the MTD or PAD of epacadostat in combination with durvalumab. More than 1 PAD may be evaluated in Phase 2. The approximate number of subjects needed for the melanoma, TNBC, and gastric and GE junction cancer cohorts will be determined using the Simon 2-stage design: Stage 1 will be the initial number of subjects per tumor type, and the decision to proceed with Stage 2 will be determined by the response rate observed in Stage 1 (further number of subjects to be enrolled in each stage per tumor type is detailed in Table 5). If more than 1 PAD is evaluated, the cohort may or may not be repeated for the specified tumor type as indicated in Table 5. The sponsor may limit enrollment of a specific tumor type to Stage 1.

Table 5: Approximate Number of Subjects by Tumor Type and Stage of Study

Tumor Type	No. of Subjects Enrolled		
	Stage 1	Stage 2 (If Study Proceeds to Stage 2)	Total (Stage 1 + 2)
Melanoma	15	25	40
TNBC	13	16	29
Gastric and GE junction cancer	9	11	20

Under Amendment 6, enrollment of the NSCLC, SCCHN, and TCC of the GU tract cohorts will be completed as expansion cohorts at the 300 mg BID dose level. The sample size for each cohort will be increased to account for the heterogeneity of PD-1 pathway–treated and PD-1 pathway–naïve subjects within the selected tumor types. The approximate number of subjects per tumor type is listed in Table 6, and the number of PD-1 pathway–treated subjects in each cohort will be limited to 10 in order to reduce the risk of any cohort having a significant imbalance between PD-1 pathway–treated and PD-1 pathway–naïve subjects, thereby preserving the predicted levels of baseline efficacy observed with PD-1 pathway monotherapy. Subjects enrolled at the 100 mg BID dose level will be analyzed independently.

Table 6: Approximate Number of Subjects for Expansion Cohorts

Tumor Type	No. of Subjects Enrolled	
	100 mg BID ^a (n = 19)	300 mg BID ^b (n = 84)
NSCLC	8	28
SCCHN	7	28
TCC of the GU tract	4	28

^a Subjects enrolled in the 100 mg BID dose level were enrolled before Amendment 5.

^b All subjects in the 300 mg BID NSCLC, SCCHN, and TCC of the GU tract cohorts enrolled in Amendment 5 or earlier are included in the total sample size.

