### 9.2. Guidelines for Decision Rules

An interim safety analysis is planned for Phase 2 after 16 subjects have been enrolled and treated for 8 weeks, and then every 3 months thereafter. If either of the following is reported during

these reviews, enrollment of subjects would be suspended until the sponsor determined the appropriate course of action and notified IRBs and regulatory authorities:

- $\geq 40\%$  of subjects report a DLT or
- $\geq 20\%$  of subjects have had a nondermatologic immune-related AE  $\geq$  Grade 3 that was attributable to the investigational agent.

Based on these rules, the probabilities of stopping a treatment group for safety is provided in [Table 14](#).

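### Protocol 9.6 leaves the denominator of its 40% pause rule undefined; read as all Phase 2 subjects, the 19 at 100 mg BID dilute the rate at 300 mg BID

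*Protocol*

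**What the plan says.** Protocol 9.6 sets the timing and scope: "An interim safety analysis is planned for Phase 2 after 16 subjects have been enrolled and treated for 8 weeks", then about every three months. The limit is 40% or more "of subjects have experienced an AE" of at least "Grade 3 that was attributable to the investigational agents". If it is crossed, "enrollment of subjects would be suspended until the sponsor determined the appropriate course of action". No dose level or tumor cohort is named.

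Protocol 4.1.2 (Table 6) lists 8 NSCLC, 7 SCCHN and 4 TCC subjects at 100 mg BID, and 28 per tumor type at 300 mg BID, the dose at which these cohorts are to be completed. Its footnote adds: "Subjects enrolled in the 100 mg BID dose level were enrolled before Amendment 5". The same section says: "Subjects enrolled at the 100 mg BID dose level will be analyzed independently". Protocol 9.4.3 bases the principal safety analysis on treatment assignment.

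SAP 9.2 has a different, two-part rule: 40% of subjects with a DLT, or 20% with a nondermatologic immune-related event of Grade 3 or higher. It states that "the probabilities of stopping a treatment group for safety is provided in" Table 14. SAP 5.3.4 defines Phase 2 treatment groups by tumor type. The SAP was written for Amendment 1 (SAP 2.1), and its only listed version is the original (SAP Table 15).

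**The concern.** A pause can protect only subjects still to be enrolled, and in these three tumor types they enter at 300 mg BID. The 100 mg group is closed. Counting it in the same percentage means an excess at 300 mg must be large enough to pull up the average of both doses before the rule acts.

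There is no external monitoring committee (Protocol 8.7, 9.5), so the numeric rule carries weight. A dose gradient is also plausible from the Protocol's own background. With ipilimumab, 300 mg BID was stopped after Grade 3 or 4 ALT/AST elevation in 5 of 7 subjects, while doses up to 50 mg BID were described as well tolerated (Protocol 1.3.1, 1.4). That was a different partner drug, so it supports plausibility and gives no rate for this combination.

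**Working it through.** **The plan's own figure.** SAP Table 14 gives operating characteristics for a 40% rule with looks at 8, 19, 30 and 41 subjects. Taking the limit as the smallest whole number of events that is at least 0.40n gives 4, 8, 12 and 17. An exact sequential binomial, stopping at the first look that reaches its limit, gives:

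| True rate | 5% | 10% | 15% | 20% | 25% | 30% | 40% |
|---|---|---|---|---|---|---|---|
| SAP Table 14 (%) | 0.0 | 0.5 | 2.3 | 7.0 | 16.4 | 32.0 | 72.5 |
| Exact (%) | 0.04 | 0.52 | 2.37 | 7.08 | 16.61 | 32.21 | 72.40 |

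The table reproduces within simulation error, so the same rounding is used below. It was built for the DLT version of the rule in one group.

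**Are the 100 mg subjects in the Phase 2 count?** 8 + 7 + 4 = 19 and 3 × 28 = 84. Adding Stage 1 of the three Simon cohorts (15 + 13 + 9 = 37) gives 19 + 84 + 37 = 140. Adding their full size (40 + 29 + 20 = 89) gives 19 + 84 + 89 = 192. The stated range of 140 to 192 is met only with the 19 included.

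**Dilution in counts.** With n subjects at 300 mg, the pooled limit is 0.40(19 + n), rounded up.
- n = 16: the pooled limit is 14 of 35. With 4/19 events at 100 mg, 9/16 (56%) at 300 mg gives 13/35 = 37% and no pause. On 300 mg alone the limit is 7/16.
- n = 84: the pooled limit is 42 of 103. The 300 mg group could reach 41/84 = 48.8% without a pause if no 100 mg subject had an event, or 37/84 = 44.0% with 4/19.

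**Chance of a pause at a single look.** With X ~ Bin(19, p100), Y ~ Bin(n, p300) and T the pooled limit, the pooled rule fires with probability Σ P(X = x) · P(Y ≥ T − x). The dose-specific rule fires with probability P(Y ≥ limit for n). The rates are assumptions: p300 = 50%, p100 = 15% to 30%.

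| n at 300 mg | Pooled limit | 300 mg limit | Pooled, p100 = 15% | Pooled, p100 = 30% | 300 mg alone |
|---|---|---|---|---|---|
| 20 | 16/39 | 8/20 | 16% | 52% | 87% |
| 28 | 19/47 | 12/28 | 29% | 64% | 83% |
| 40 | 24/59 | 16/40 | 42% | 72% | 92% |
| 84 | 42/103 | 34/84 | 76% | 89% | 97% |

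**False pauses.** The same formulas apply, with equal true rates at both doses and a single look.

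| True rate | n at 300 mg | 300 mg alone | Pooled |
|---|---|---|---|
| 25% | 20 | 10% | 2% |
| 25% | 28 | 3% | 1% |
| 30% | 20 | 23% | 9% |

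Over five looks (20, 28, 40, 60 and 84 at 300 mg), false pauses are about 11% on 300 mg alone against 3% pooled at a true 25%, and 28% against 13% at a true 30%.

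**The case against.** The strongest reply is that Protocol 9.6 never says the doses are pooled. That is correct: pooling is an inference, though the natural one, because the look is planned for Phase 2 as a whole and the Phase 2 total includes the 19. The sentence on independent analysis of the 100 mg subjects and the grouping in Protocol 9.4.3 both lean toward separation, but neither is tied to the pause rule.

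The size also depends on unsourced rates. Masking needs a lower rate at 100 mg, and it shrinks as 300 mg enrollment grows. Under the 15%/50% assumption, the pooled rule fires about 79% of the time over the five looks used above. The doses in the melanoma, TNBC and gastric/GE junction cohorts are not stated. If all were 300 mg and the 100 mg rate were 20%, the observed 300 mg rate needed would be (0.40 × 140 − 3.8)/121 = 43.1%, or (0.40 × 192 − 3.8)/173 = 42.2%. These limits stand.

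A reader might infer that this is the only numeric safety stop. The documents do not support that, because SAP 9.2 still carries a 20% immune-related limit that has not been reconciled with the Protocol. A reader might also take the SAP's reference to a treatment group as support for a split by dose. It is not, since Phase 2 groups there are tumor types. Under that grouping the diluting counts are 8, 7 and 4. With 28 at 300 mg and 20% at 100 mg, the rates needed are (15 − 1.6)/28 = 47.9%, (14 − 1.4)/28 = 45.0% and (13 − 0.8)/28 = 43.6%. The dilution is smaller but still present.

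Finally, the approximately weekly calls in Protocol 8.7 review cohort-specific data. They are a real but partial safeguard, because they carry no numeric limit.

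**Conclusion.** The concern holds as a gap in definition with a foreseeable consequence. Protocol 9.6 does not fix its denominator, and no other section supplies one by dose. On the natural reading, the rule is least sensitive at 300 mg BID just after that expansion starts, when a pause would protect the most future subjects. Under the assumed rates, the single-look loss with 20 subjects at 300 mg is from 87% to between 16% and 52%; by 84 subjects it is from 97% to between 76% and 89%. The conclusion rests on the pooled reading and on a lower event rate at 100 mg, neither of which the documents state. They do not show that any excess was hidden, or how the reviews were run in practice.

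**What to change.** State in Protocol 9.6 which subjects form the denominator. Apply the existing 40% threshold to each dose level once that dose has the plan's minimum of 16 treated subjects, and keep the overall check. No threshold or dose changes. Reconcile 9.6 with SAP 9.2: replace or explicitly retain the two-part rule, say whether groups are tumor types or dose levels, and give operating characteristics for the rule in force.

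The text change is a sentence or two in the Protocol and a SAP update. The statistical cost is the extra false pauses shown above, which are concentrated at small n and accumulate over repeated looks. Testing each dose as well as the total would add somewhat more. A pause suspends enrollment pending sponsor review and notification, so the cost of a false one is limited.
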